2. Recruitment. We will recruit participants through posted flyers, e-mail, electronic and newsprint advertisements (e.g. campus student and faculty/staff newspapers, local and regional newspapers; see attachment “*Advertisements*”), and word of mouth. The posted advertisements will instruct interested participants to call the study center ([name] Laboratory, Department of Human Sciences) or complete an online pre-screening survey to obtain further information. During the phone-in hours, a trained individual (i.e. project coordinator or graduate assistant) will be available to describe the study and determine preliminary qualification by conducting a scripted phone interview (e.g. do you take dietary supplements?, do you smoke?; see “*Phone Script*” attachment). The individual will record answers and assess whether the person calling is likely or not to be an acceptable study participant. If the caller and the interviewer agree that the caller should participate, the prospective participant will be invited to a screening meeting, where the study will be fully described, and the individual will be provided a consent form to complete prior to any involvement in the study procedures. Data collected during this phase will include participant’s age, health status, physical activity, and contact information (see “*Informed Consent*” attachment).

3. Power Calculation and Data Analysis. [name] (biostatistician; *co-PI and Dept of Biomedical Informatics*) performed a power analysis. To ensure that the order by which each participant completes each trial is randomized, a random sequence generator (<http://www.random.org/sequences/>) will be used to determine the order by which each participant will undergo the two trials. We will primarily compare the

within-subject changes (WWB endpoint vs. WB endpoint) between high-responders and low-responders. We anticipate to have 6-12 high-responders and 5-10 low-responders of the total 40 study participants to achieve 80% power to detect a 1.6-fold difference in the changes of postprandial glucose levels (AUC from 0 to 180 minutes) between high-responders and low-responders, at the expected coefficient of variation (CV) 0.5 at a significant level of 0.05.

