Mixed effect modeling will be performed, diet and time will be included as fixed factors while participant serves as a random factor. False discovery rate (FDR) will be used to control type I error rate for microbiome and metabolome data, while the Bonferroni method will be applied for other measures (e.g., inflammatory markers). Data will be first normalized before analysis. Spearman correlations will be calculated to define associations between microbes, inflammatory genes, metabolites that show significant changes in highresponders.

To test whether the changes in microbes after WWB intake associate with the biological response, logistic regression will be fitted to each of the potential microbes or as a combination. We will also couple the logistic regression with receiver-operating characteristic (ROC) analysis to evaluate the specificity and sensitivity of the microbes that predict participants' biological response, and the area under the curve (AUC) of the microbial model will be displayed. Data analysis will be performed in R (open resource) or SAS (SAS, Inc; Cary, NC). The sample size was calculated in PASS 20 (NCSS, LLC; Kaysville, Utah).

C. Measurement/Instrumentation

All procedures will take place in the Human Nutrition Program located in Evans Laboratory. Infrastructure that is present includes a metabolic research kitchen, a private office to meet with participants, a clinical research laboratory for performing phlebotomy and research procedures, and a separate biochemical laboratory for processing and preserving biological specimens.

1. *Anthropometric Parameters and Blood Pressure.* At screening, day 1, 7, and 14, participants will rest for 15 minutes prior to determining blood pressure using an automated blood pressure cuff. BMI will be calculated from height determined from a wall-mounted stadiometer and weight from a calibrated scale.

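### The logistic regression of response on microbes has no safeguard against separation; if fitted to the 11-22 high- and low-responders, it can give infinite odds ratios and unreliable p-values

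*Combined protocol and SAP*

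**What the plan says.** Section VI.B.3 (Power Calculation and Data Analysis) introduces the model with this purpose: "To test whether the changes in microbes after WWB intake associate with the biological response". The method is that "logistic regression will be fitted to each of the potential microbes or as a combination". A companion analysis follows: "We will also couple the logistic regression with receiver-operating characteristic (ROC) analysis". Software is R or SAS.

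On group sizes, the same section states: "We anticipate to have 6-12 high-responders and 5-10 low-responders of the total 40 study participants". That sentence belongs to the power calculation for glucose, where the plan contrasts "within-subject changes (WWB endpoint vs. WB endpoint) between high-responders and low-responders".

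On multiplicity: "False discovery rate (FDR) will be used to control type I error rate for microbiome and metabolome data". This stands in the mixed-model paragraph.

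The plan does not name a coefficient test (Wald, likelihood-ratio or score), a penalised or exact fit, a limit on the number of microbes in a combination, or what to do when a fit fails to converge. It also does not say whether the logistic model uses only the two responder groups or all 40 participants.

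**The concern.** Maximum-likelihood logistic regression has no solution when a predictor, or a linear combination of predictors, splits the two outcome groups without overlap. The slope runs to infinity. In 11 to 22 people this can happen through a strong real effect, or by chance once several microbes enter together.

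The test then matters a great deal. The Wald p-value, which standard R and SAS coefficient tables print, goes towards 1 because the standard error grows faster than the estimate. A microbe that discriminates perfectly would look like one that does nothing.

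Section II.D makes it a stated aim to learn whether differences in gut bacteria explain who benefits, and this model is the plan's direct test of that. This is a fault in the estimate and test themselves. It is distinct from optimism in the ROC curve, and cross-validation would not remove it.

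**Working it through.** **The plan's own figure.** The documents give no operating figure for the logistic model. The only stated figure is 80% power for the glucose comparison. Taking a 1.6-fold difference and CV 0.5 on the raw scale, delta/SD = 0.6/0.5 = 1.2. Two-sided normal approximation:
- 12 v 10: 1.2/√(1/12 + 1/10) = 2.80; 2.80 − 1.96 = 0.84; power 0.80.
- 6 v 5: 1.2/√(1/6 + 1/5) = 1.98; 1.98 − 1.96 = 0.02; power 0.51.

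So the stated power is met only at the top of the range. That is a separate matter, but it shows that 12 v 10 and 6 v 5 are both live scenarios under the plan.

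**Inputs.** Groups of 6-12 and 5-10 come from section VI.B.3; 9 v 7 is an intermediate case. Assumptions: independent Gaussian taxa; combinations of 5, 8 or 10 taxa; 200 taxa where a count is needed; test level 0.05.

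**One microbe separating the groups.** The log-likelihood rises towards 0 as the slope grows, so there is no finite maximum. The likelihood-ratio statistic is therefore −2 × (null log-likelihood):
- 6 v 5: −2 × [6 ln(6/11) + 5 ln(5/11)] = 15.16, p ≈ 1e-4.
- 12 v 10: −2 × [12 ln(12/22) + 10 ln(10/22)] = 30.32, p ≈ 4e-8.

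At given group sizes, every separating microbe gets this same value. In simulated separated data (true shift 3 SD) the median results were:

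| Groups | Wald p | Likelihood-ratio p | Firth odds ratio per SD | Firth penalised likelihood-ratio p |
|---|---|---|---|---|
| 6 v 5 | 0.9995 | 1e-4 | about 22 | about 0.002 |
| 12 v 10 | 0.999 | 4e-8 | about 126 | about 3e-6 |

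**Power for one microbe with a true shift** (1,000 datasets per cell):
- 6 v 5: Wald at most 0.3% at shifts of 1 to 3 SD; ordinary likelihood ratio about 90% at 2 SD and nearly 100% at 3 SD.
- 9 v 7: Wald about 34% at 2 SD and 10% at 3 SD; likelihood ratio 97% and 100%.
- 12 v 10: Wald about 75% at 2 SD and 30% at 3 SD; likelihood ratio at least 99%.

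**Null rejection.** At 6 v 5, separate simulation runs put the ordinary likelihood-ratio test between 7.6% and about 10%. A check with 2,000 null datasets per cell gave 8.5% (6 v 5), 7.5% (9 v 7) and 6.4% (12 v 10). Firth with the penalised likelihood-ratio test gave about 4 to 6%.

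**How often separation occurs.**
- Single noise microbe: 2/C(11,5) = 2/462 = 0.43% at 6 v 5; 2/C(22,10) = 2/646,646 ≈ 3e-6 at 12 v 10. With 200 independent taxa at 6 v 5, the chance that at least one separates is 1 − (1 − 0.0043)^200 ≈ 58%.
- Single microbe with a true shift of 1, 2 or 3 SD: 6%, 33%, 74% at 6 v 5; 0.1%, 7%, 44% at 12 v 10.
- Combinations of noise taxa (linear-programming check):

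| Taxa | 6 v 5 | 9 v 7 | 12 v 10 |
|---|---|---|---|
| 5 | about 55% | about 11% | about 1% |
| 8 | about 98% | about 65% | about 17% |

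If all 40 participants are used, ten noise taxa separate 6 v 34 in about 22% of datasets and 12 v 28 in about 1%.

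**FDR at 6 v 5.** With 200 taxa, the first Benjamini-Hochberg step requires p ≤ 0.05/200 = 0.00025. The smallest Firth p-value seen was about 0.001. At a median p of 0.0024, about ten such taxa would be needed, since 10 × 0.00025 = 0.0025.

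**The case against.** The strongest reply is that the plan never says it will use Wald tests. A reader might infer that the stated method discards the best microbes; the documents do not support that, because a likelihood-ratio test on the same data gives them very small p-values. This stands, and the Wald result is conditional. It does not rescue the plan, since the ordinary likelihood-ratio test still leaves an infinite odds ratio and rejects too often under the null in the smallest groups.

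Second, the figure of 11 to 22 people is attached to the glucose comparison, not to this model. Section IV also allows response to be redefined with other markers if too few responders emerge. This stands too: the two-group set is the natural reading, not a stated one, and with all 40 participants separation is much rarer.

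Third, a reader might infer that separation is an everyday event here. That is too strong for single microbes in the larger groups: at 12 v 10 a noise microbe almost never separates, and a real one does so often only at shifts near 3 SD. The high percentages belong to small groups and to combinations, whose size the plan does not give. The count of 200 taxa is likewise assumed, and the candidate list may be shorter.

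Fourth, the change of method does not by itself carry a lone separating microbe through FDR control at 6 v 5. This is correct and is a sample-size limit. Applying FDR to the logistic p-values is also an inference from where that sentence sits.

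Finally, the ROC analysis would show a separating microbe as an apparent area of 1, so it would not vanish unseen. For a combination that separates by chance, however, that area carries no information.

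**Conclusion.** The concern holds as a gap in specification with material consequences, conditional on the analysis set and the test. If the model is fitted by ordinary maximum likelihood to the anticipated responder groups, separation leaves no finite odds ratio, and neither ordinary test is satisfactory. Wald tests have about 0% power at 6 v 5 and lose power as the effect strengthens at 12 v 10. Ordinary likelihood-ratio tests reject about 8-10% under the null at the small end, easing to about 6% at 12 v 10.

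Chance separation is chiefly a risk for combinations and small groups. The sizes rest on independent Gaussian taxa, assumed combination sizes and use of the two extreme groups only. The documents do not establish that Wald tests are planned, that single-microbe separation is common across the whole range of group sizes, or that the strongest microbes will be lost. The remedy is cheap and better behaved than either default, so the change should be made.

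**What to change.** In section VI.B.3:
- For single microbes, specify Firth-penalised logistic regression with penalised likelihood-ratio p-values and profile-likelihood intervals.
- For combinations, specify ridge or elastic-net logistic regression, and state how many microbes may enter.
- State that Wald p-values will not be used.
- State whether the model includes only the high- and low-responders or all 40 participants, and whether FDR control applies to these p-values.

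The cost is a software option in R or SAS and a few sentences; no data collection changes. Estimates shrink slightly towards no effect. The change does not create information: at 6 v 5 a lone separating microbe, with p about 0.001 at best, may still not survive FDR control over many taxa, and the plan should say so.

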specifically compare the gut microbiota composition of prediabetes subjects who exhibited improved glucose metabolism following the WWB diet with those who responded least to this dietary intervention to determine if differences in gut bacteria could explain the beneficial effect of WWB in some individuals.

III. Anticipated Results

We expect to achieve >95% compliance (based on in-house observations of test meal consumption, returned foods, and circulating biomarkers of WWB intakes, e.g., alkylresorcinol concentrations of 19:0, 21:0, and 23:0) without any adverse effects or changes in body mass or energy intakes.

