6. *Gut Permeability.* On day 14 of each intervention, fasted participants will ingest a glucose solution (75 g; oral glucose tolerance test) containing 4-sugar probes [lactulose (5 g), mannitol (1 g), sucralose (1 g), and erythritol (1 g)] as described.^{59, 60} Urinary sugars will be assessed by LC-MS as we established.⁵⁹ Sugar excretion (%), and excretion ratios of sugars from 0-5 h (lactulose/mannitol) and 6-24 h (sucralose/erythritol) will be calculated to reflect upper and lower gastrointestinal permeability, respectively.⁶¹⁻⁶⁴ This approach is based on lactulose being absorbed in the small intestine, but not the colon, whereas sucralose is absorbed in the colon.⁶⁵ Thus, these studies will define site-specific gut permeability, and the benefit of WWB treatment.

7. *Microbiota Composition.* Microbiota composition and the predicted functional metagenome will be assessed from fecal samples provided on day 14 of each intervention arm as previously described.⁶⁶⁻⁷⁰ Effects of WWB (vs WB) on total bacterial abundance will be determined by qPCR.⁷¹ Microbiota will be characterized for diversity and community structure by sequencing 16S rRNA genes using MiSeq. Bacteria will be identified by comparing sequences representing each operation taxonomic unit (OTU) with RDP and Silva databases.^{72, 73} α -Diversity (OTU richness, Shannon-Wiener diversity index, evenness) will be calculated using Qiime. Comparisons of diversity among samples (β -diversity) will be performed using the Bray-Curtis dissimilarity,⁷⁴ followed by multivariate analyses (e.g. principle coordinate analysis, permutational multivariate analysis of variance, analysis of similarity, partial least square discriminant analysis). The functional metagenome will be predicted using PICRUSt⁷⁵ and PanFP⁷⁶ based on reference genome databases and the KEGG Orthology classification scheme to obtain a functional gene abundance matrix.

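### PERMANOVA and ANOSIM are listed without a dispersion test; on small, unequal responder groups a difference in spread could be read as a difference in composition, or a real shift missed

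*Combined protocol and SAP*

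**What the plan says.** Section VI.C.7 (Microbiota Composition) says that comparisons between samples "will be performed using the Bray-Curtis dissimilarity", followed by multivariate analyses introduced as examples. These include "permutational multivariate analysis of variance, analysis of similarity", next to ordination and a discriminant method. The paragraph does not say which groups the tests compare. The only contrast it names is WWB v WB, for total bacterial abundance by qPCR. No dispersion test, heterogeneity-robust statistic or rule for reading a significant result appears there or elsewhere.

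The aim in Section II.D is to "specifically compare the gut microbiota composition of prediabetes subjects who exhibited improved glucose metabolism following the WWB diet with those who responded least", and "to determine if differences in gut bacteria could explain the beneficial effect of WWB in some individuals".

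Section VI.B.3 gives the group sizes: "We anticipate to have 6-12 high-responders and 5-10 low-responders of the total 40 study participants". It also states that "False discovery rate (FDR) will be used to control type I error rate for microbiome and metabolome data", and it plans logistic regression and ROC analysis of microbes against response.

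**The concern.** The question in Section II.D is whether the two responder groups sit in different places in community space. Shuffling group labels tests a wider null, in which the groups have the same location and the same spread. ANOSIM compares ranked between-group with within-group distances and responds to spread even with equal group sizes. PERMANOVA pools the within-group variation and responds to spread when sizes are unequal. Responder group sizes are set by who responds, so unequal splits such as 12 v 5 lie within the plan.

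Unequal spread is plausible, because Section III expects WWB to alter composition in only some participants, but no ratio or direction is given. At stake is a statement that responders carry a different microbiota when one group may only be more variable. The opposite error is also possible: if the larger group is the more variable one, both tests become conservative. FDR control addresses multiplicity and cannot separate location from spread.

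**Working it through.** **The plan's own figure.** The only power statement concerns glucose AUC: "to achieve 80% power to detect a 1.6-fold difference", "at the expected coefficient of variation (CV) 0.5 at a significant level of 0.05". Taking a difference of 0.6 and an SD of 0.5 (in units of the low-responder mean) at 12 v 10, SE = 0.5 × √(1/12 + 1/10) = 0.214. Then 0.6/0.214 − 1.96 = 0.84, which gives 80% power (two-sided normal approximation). At 6 v 5 the same formula gives 51%. So 80% is reached only at the top of both ranges. This figure says nothing about the community tests, and the point here does not rest on it.

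**Inputs.** Group sizes come from VI.B.3. The tests and distance come from VI.C.7. The spread ratio of 1.5 and the number of axes are assumptions.

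**Statistics.** With SS_T = Σd²/N over all pairs and SS_g = Σd²/n_g over pairs within group g:
- PERMANOVA: F = (SS_T − SS_1 − SS_2) / [(SS_1 + SS_2)/(N − 2)].
- ANOSIM: R = (mean between-group rank − mean within-group rank) / [N(N − 1)/4].
- Welch-type W*d: [(SS_T − SS_1 − SS_2) × N/(n_1 n_2)] / (s_1²/n_1 + s_2²/n_2), where s_g² = SS_g/(n_g − 1).

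**Why group size matters for PERMANOVA.** Take identical centroids, with variance per axis of 1 in one group and 1.5² = 2.25 in the other. Compare the true variance of the centroid difference with the variance that pooling implies.
- 12 v 5, smaller group wider: true 1/12 + 2.25/5 = 0.533; pooled [(11 × 1 + 4 × 2.25)/15] × (1/12 + 1/5) = 1.333 × 0.283 = 0.378. The ratio is 1.41, so F is too large.
- 12 v 5, larger group wider: true 2.25/12 + 1/5 = 0.388; pooled [(11 × 2.25 + 4 × 1)/15] × 0.283 = 1.917 × 0.283 = 0.543. The ratio is 0.71, so F is too small.
- 12 v 10, smaller group wider: true 1/12 + 2.25/10 = 0.308; pooled [(11 + 9 × 2.25)/20] × (1/12 + 1/10) = 1.5625 × 0.183 = 0.286. The ratio is 1.08.
- Equal sizes: the ratio is 1.

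**Simulated rejection at nominal 5%.** There is no location difference, the data are Gaussian with 3 to 10 axes, there is one sample per person, and the group listed second is 1.5 times more spread.

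| Sizes | PERMANOVA | ANOSIM | W*d |
|---|---|---|---|
| 12 v 5 | about 12-22% | about 44-88% | about 5-6% |
| 12 v 10 | about 6-7% | about 36-81% | about 5-6% |
| 8 v 8 | about 5-6% | about 11-27% | about 5-6% |

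With 20 axes, PERMANOVA and ANOSIM reject 29.9% and 98.8% at 12 v 5, and 9.6% and 97.6% at 12 v 10. With equal spread both hold about 4-7%. If the larger group at 12 v 5 is the wider one, both reject about 1% or less. Over all Euclidean runs, including spread ratio 2, W*d stayed at about 4-7%.

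**Power.** At 12 v 5 with 10 axes, a 2-SD shift on one axis and the larger group 1.5 times wider, power is 20-21% for PERMANOVA, 0.4% for ANOSIM and 49-50% for W*d.

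**On Bray-Curtis.** In a Dirichlet model with equal mean proportions at 12 v 5 (mean within-group distance 0.48 v 0.58), PERMANOVA rejected 35%, ANOSIM 97% and W*d 12%. In a second such model PERMANOVA rejected 17-69% even at 10 v 10. Under Bray-Curtis a change in concentration also moves the centroid, so these rates are not pure false positives. The Gaussian case is the clean test of location against spread.

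**Diet contrast.** With 40 pairs, within-person label swaps and 1.5 times the within-person spread in one arm, PERMANOVA rejected 4% and ANOSIM 76%.

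**The case against.** The strongest reply is that the plan never assigns these tests to the responder groups. That is correct: VI.C.7 names no groups, and the link to II.D is an inference. The tests are listed as examples, so a dispersion check is unplanned rather than excluded. The methods papers cited there cannot be seen, and an ordination plot can show spread.

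A reader might infer that the study's central microbiota claim hangs on PERMANOVA and ANOSIM. The documents do not support that. VI.B.3 makes the primary comparison one of glucose AUC and examines microbes against response by logistic regression and ROC analysis. Those analyses do not use between-group distances and are unaffected.

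A reader might also infer that PERMANOVA is unsound throughout. It is not: in the Euclidean model it departs from its level only when both sizes and spread are unequal, and it stays nominal for WWB v WB.

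Finally, the rates depend on assumptions. The documents give no spread ratio, and the number and relative size of the axes move the results a good deal. At 12 v 5 and ratio 1.5, ten equal axes give ANOSIM about 85-88% and three give about 44%. The high rates are therefore the upper part of a range. What stands is that ANOSIM over-rejects across that range, and that PERMANOVA does so in the more unequal splits the plan allows.

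**Conclusion.** The point holds conditionally and is a cheap improvement, not a defect that undermines the design. If PERMANOVA or ANOSIM is applied to high- v low-responders at the anticipated sizes, and the groups differ in spread, the result cannot be read as a difference in composition. At an assumed ratio of 1.5 with the smaller group wider, PERMANOVA's error ranges from near nominal (8 v 8, 12 v 10) to roughly one in five (12 v 5, ten axes). ANOSIM's ranges from about 11% to 88% over the same sizes and 3 to 10 axes. If the larger group is the wider one, the loss is in power. With equal spread there is no problem.

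It would go too far to treat a Welch-type test as sufficient on its own for a composition claim. On the planned Bray-Curtis distance it still rejected 12% in one run with equal mean proportions.

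**What to change.** In VI.C.7:
- State which contrasts the community tests serve.
- Use ANOSIM descriptively only, not for inference.
- Report a multivariate dispersion test (PERMDISP) beside every PERMANOVA.
- For the unequal responder groups, add the Welch-type distance-based permutation test (W*d) and base the inference on it.
- Where the dispersion test is also significant, report a difference in composition and/or variability, not composition alone.
- State that W*d is close to nominal in Euclidean simulations (about 4-7%) but not exact on Bray-Curtis, where spread and location do not separate cleanly.

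This takes a few sentences and a few lines of R, with no new data. W*d costs about 2-3 points of power at 12 v 5 with equal spread. When the smaller group is the wider one, it detects a true shift less often than PERMANOVA appears to (28% v 67% in the 20-axis run at 12 v 5), but PERMANOVA already rejects 30% there with no shift. The dispersion test will have low power at these sizes, so a non-significant result does not show equal spread.
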